7.5 SECONDARY ENDPOINTS

7.5.1 Key secondary endpoint

This section is not applicable as no key secondary endpoint has been specified in the protocol.

7.5.1.1 Primary analysis of the key secondary endpoint

7.5.1.2 Sensitivity analysis, subgroup analysis, exploratory analysis of the key secondary endpoint

7.5.2 (Other) Secondary endpoints

Analysis of all secondary endpoints will be performed using the ITT population.

Proprietary confidential information © 2021 Boehringer Ingelheim International GmbH or one or more of its affiliated companies

For the secondary endpoints listed below, the pairwise comparison of observed proportion of patients at each dose level will be compared to placebo using the same methods outlined for the primary endpoint.

- Proportion of patients with confirmed CRR without renal flare
- Proportion of patients with proteinuria <0.8g/d and without any renal flares
- Proportion of patients with CRR and sustained steroid reduction to ≤ 5 mg/d without renal flare
- Proportion of patients experiencing at least one renal flare
- Proportion of patients with partial renal response (PRR) without renal flare

At the time this TSAP was prepared, 8 renal flares were known to have occurred. The secondary endpoint, time to renal flare, will be displayed using a Kaplan Meier curve across all treatment groups to explore the timing of renal flares with color-coding, symbols or an embedded table to indicate the treatment group in which they occurred.

For the secondary endpoint, change from baseline in the SLEDAI, descriptive statistics will be provided.

Due to the perceived importance of the secondary endpoint, confirmed CRR, the logistic analyses described for the primary analysis will be performed and the sensitivity analyses by race and by proteinuria at screening in 1293.10 will be performed.

The analysis of proportion of patients with CRR having sustained steroid reduction ≤ 5 mg from week 26 will be repeated for confirmed CRR. The proportion of patients with confirmed CRR or confirmed PRR will be analysed. The analysis of proportion of patients with CRR who were steroid free from week 26 will be repeated for confirmed CRR. The exploratory analysis combining 180mg and 240mg BI 655064 versus placebo will be repeated for confirmed CRR.

At the time this TSAP was prepared, the expectation is that confirmed CRR will be more sensitive than the primary endpoint for detecting treatment effects within subgroups. For this reason, the secondary endpoint, confirmed CRR, will be used for exploring treatment effects within subgroups.

Time since diagnosis (of LN) was identified in trial 1293.10 as prognostic of obtaining CRR. A subgroup analysis of confirmed CRR will be performed based on the ITT, defined by time since diagnosis at the time of entry to 1293.10. One group will include those patients with time of diagnosis from 0- < 6 months. The second group will include patients with time of diagnosis ≥ 6 months.

[figure not shown]
A subgroup analysis of confirmed CRR at week 52 will be performed based on the ITT data set, defined by proteinuria at baseline. An important CTP inclusion criterion in 1293.10 was active renal disease evidenced by proteinuria ≥ 1.0 g/day [(UP/UC) ≥ 1] at screening. However, by baseline, there were patients for whom UP and/or UP/UC determined from 24h

Proprietary confidential information © 2021 Boehringer Ingelheim International GmbH or one or more of its affiliated companies

urine collections were < 1.0 g/day. Subgroups will be created based on the UP from the 24h collections at baseline. One group will include patients with UP < 1.0 g/day. The second group will include all other patients.

Subgroup analyses of confirmed CRR at week 52 will be performed based on the ITT data set stratified using biopsy-derived disease activity index and chronicity index scores. The scoring was performed by a renal pathologist who evaluated biopsy slides submitted by the sites. Subgroup analyses will be performed based on the activity score and on the chronicity score. The median score will be used as the cut-point to split the patients into one group with scores less than the median versus the group with scores greater than or equal to the median.

Graphical displays will be used to explore relationships between biomarkers and clinical endpoints. The biomarkers were determined from samples obtained at Week 26 of 1293.10. Five biomarkers were selected for this exploratory analysis based on meaningful post-treatment decreases from baseline distinguishing these biomarkers from other biomarkers observed. Individual patient change from baseline for the biomarker, change from baseline in SLEDAI score and confirmed CRR status will be displayed. The biomarkers from 1293.10 will be displayed with SLEDAI scores and confirmed CRR status. In each figure, the clinical endpoints will be from the same time points with separate figures for 1293.10 - Weeks 26, 1293.10 – Week 52 and 1293.13- Week 52.

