5.2.2 Secondary endpoints

The secondary endpoints were re-ordered in order of perceived importance as follows:

[figure not shown]
- Proportion of patients with confirmed CRR (defined as CRR at both week 42 and week 52 using UP/UC from spot urine) without renal flare
The endpoint, confirmed CRR, was introduced as a post hoc endpoint for 1293.10 where it proved to be a more sensitive endpoint as it was able to detect treatment effect in the presence of an unexpected large placebo response. With the requirement to demonstrate CRR at both time points, the placebo effect at Week 52 was reduced resulting in meaningful response rates for 180 mg and 240 mg BI655064.
- Proportion of patients with proteinuria <0.8g/d and without any renal flares at week 52.
- Proportion of patients with CRR at week 52 and sustained steroid reduction to ≤5 mg/d from week 26 to week 52.
- Proportion of patients experiencing at least one renal flare during 52 weeks
- Time to first renal flare over the course of 52 weeks.
- Proportion of patients with PRR without renal flare derived from UP 24h collection at Week 52.
Although not included in the list of endpoints in the CTP, PRR is defined in the CTR along with CRR as an assessment of renal response.
It is defined as at least 50% reduction of proteinuria from baseline and **either** eGFR within normal range at time of assessment or decrease of eGFR < 20% from baseline if eGFR below normal range at time of assessment.
- Change from baseline in SLEDAI at weeks 12, 26, 42 and 52.
- Proportion of patients with CRR at Week 52.
It was decided that CRR alone without consideration of whether a patient experienced a renal flare was not appropriate as the occurrence of a flare indicates the patient was not a responder. This endpoint will not be analysed.

Proprietary confidential information © 2021 Boehringer Ingelheim International GmbH or one or more of its affiliated companies

Proprietary confidential information © 2021 Boehringer Ingelheim International GmbH or one or more of its affiliated companies

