6.3 SUBJECT SETS ANALYSED

- **Randomised set:**
This patient set includes all randomised patients, whether treated or not.
- **Treated set:**
This patient set includes all patients who were dispensed study medication and were documented to have taken at least one dose of investigational treatment.
- **Intent to treat (ITT) set:**
This patient set includes all patients from the treated set who have a baseline (or screening) proteinuria (spot urine can be a used if patient does not have 24-hour collections) and baseline or screening eGFR

[figure not shown]
The Per protocol set (PPS) was dropped with the second CTP amendment.

Proprietary confidential information © 2021 Boehringer Ingelheim International GmbH or one or more of its affiliated companies

Table 6.3: 1 Subject sets analysed

Class of endpoint	Patient set		
	Treated set	ITT	
Primary endpoint: CRR at week 52		X	
Secondary endpoints		X	
Safety endpoints	X		
Demographic/baseline endpoints	X		

Note that the number of patients with available data may differ across endpoints. For details, see [Section 6.6](#) “Handling of missing data”.

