For secondary and further endpoints based on proteinuria and eGFR, the same imputation rules will be applied to derive response at weeks 26 and 52.

Definition/derivation of CRR for patients who prematurely stop trial medication (not applicable to unblinded Placebo patients who obtained BI approval to stop injections)

The CTP specified that as an imputation technique to deal with missing data, for the analysis of primary and CRR-related secondary endpoints, non-completers considered failure will be used. To determine if this was a reasonable approach, the trial team reviewed the patients who discontinued early, including review of reasons for early treatment discontinuation, AEs, concomitant meds, renal labs. The following handling rules better fit the circumstances around treatment discontinuation & were adopted.

- (1) If the details around the early discontinuation of trial medication indicated that the patient discontinued due to worsening renal function, had a renal flare or needed rescue medication, then CRR & PRR will be defined as ‘Non-responder’.
- (2) If there was no discernable worsening of renal function & the patient had a reasonable treatment duration, renal tests at the time of treatment discontinuation will be used to derive CRR & PRR.
- (3) If neither of the above applies and if at the time of discontinuation, the patient could have been considered a responder, then the patient was considered censored or non-evaluable. If the patient discontinued before Week 26, then both Week 26 & Week 52 are non-evaluable. If the patient discontinued after Week 26, then CRR & PRR were derived for Week 26 & Week 52 is non-evaluable.

Proprietary confidential information © 2021 Boehringer Ingelheim International GmbH or one or more of its affiliated companies

For patients who took study drug for < 42 weeks, continued to participate in the trial and have urine collections and serum creatinine determinations, their data will be displayed in a separate listing.

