6.6.2 Other endpoints and safety endpoints

With respect to the SLEDAI, no missing item(s) will be imputed. If one item comprising the sub-score is missing, the sub-score will be set to missing. Other sub-scores will be derived and analysed. If one item is missing, the total score will be set to missing.

Missing or incomplete AE dates are imputed according to BI standards (see “Handling of missing and incomplete AE dates”). [\(1\)](#)

All other endpoints will be analysed without imputing for any missing data.

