7. PLANNED ANALYSIS

For End-Of-Text (EoT) tables, the set of summary statistics is: N / Mean / SD / Min / Median / Max.

For tables that are provided for endpoints with some extreme data, median, quartiles and percentiles should be preferred to mean, standard deviation, minimum and maximum.

Tabulations of frequencies for categorical data will include all possible categories and will display the number of observations in a category as well as the percentage (%) relative to the respective treatment group (unless otherwise specified, all patients in the respective patient set whether they have non-missing values or not). Percentages will be rounded to one decimal place. The category missing will be displayed only if there are missing values.

All calculated statistics will be presented to one more decimal place than the original measurement accuracy of the variable being summarised.

All p-values will be displayed to four decimal places (or “<0.0001” if appropriate).

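### The 52-week renal flare proportion has no rule for patients whose renal observation ends early without a flare, and no by-arm estimate that allows for censoring

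*SAP*

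**What the plan says.** - **Endpoint.** SAP 5.2.2 lists "Proportion of patients experiencing at least one renal flare during 52 weeks". Time to first flare is a separate secondary endpoint.
- **Set and method.** SAP 7.5.2 states: "Analysis of all secondary endpoints will be performed using the ITT population". It names "Proportion of patients experiencing at least one renal flare" among the endpoints whose observed proportion at each dose is compared with placebo by the primary-endpoint methods. For observed proportions, SAP 7.4.1 specifies Newcombe intervals and Barnard tests, with nominal p-values and a two-sided cut-off of 0.20.
- **Denominator.** SAP 7 sets the base for percentages as "unless otherwise specified, all patients in the respective patient set whether they have non-missing values or not". The note under Table 6.3: 1 adds: "Note that the number of patients with available data may differ across endpoints".
- **Early stopping.** The three rules in SAP 6.6.1 for patients who stop trial medication early define CRR and PRR. One of them makes some patients censored or non-evaluable, but spells out the consequence for CRR and PRR only. Other endpoints built on proteinuria and eGFR come under the missing-data rules only for response at weeks 26 and 52.
- **Everything else.** SAP 6.6.2: "All other endpoints will be analysed without imputing for any missing data".
- **Data after stopping.** For patients with less than 42 weeks on drug who "continued to participate in the trial and have urine collections and serum creatinine determinations, their data will be displayed in a separate listing". Protocol 6.2.3.3 invites all early stoppers to visits at weeks 12, 26, 42 and 52 with serum creatinine and spot urine.
- **Time to flare.** SAP 7.5.2 plans one Kaplan-Meier curve across all treatment groups, with a marking to show the arm of each flare. It reports 8 flares known at the time of writing.
- **Flare definition.** Protocol 5.1.1 requires confirmation by a repeat test within 2 weeks. Its first criterion places the rise in proteinuria within the treatment period, and its second uses the same limit for the preceding improvement.

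**The concern.** A flare can be found only while proteinuria and creatinine are being measured. A 52-week risk estimated as flares over all ITT patients is therefore right only if everyone is observed to a flare or to week 52. The SAP has no rule for patients who are not. The protocol's rule that non-completers count as failures (protocol 7.5) covers the primary and CRR-related endpoints, so it does not fill the gap.

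The comparison with placebo is at stake. If one arm loses more observation time than another, its flare proportion moves for a reason unrelated to treatment. Unequal exit is plausible here. On 20 October 2020, 29 patients were unblinded, 20 of them on treatment, and investigators were asked to discuss continued participation with them. SAP 6.6.1 also exempts from its early-stop rules unblinded placebo patients who had approval to stop injections.

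**Working it through.** **Inputs.** From the documents: 8 known flares in all arms together (SAP 7.5.2) and about 60 expected patients (protocol 7.7, a roll-over estimate). The plan gives no expected flare rate, no power and no stopping rates by arm, so it has no figure to reproduce. The risks and exit rates below are assumptions.

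**Model.** Constant flare hazard, leaving unrelated to flare risk, and no renal data after leaving. Let p be the true 52-week risk, d the share that leaves early, and L = -ln(1 - p). For leaving times uniform over 52 weeks, the chance of a flare before leaving is g = 1 - (1 - e^(-L))/L = 1 - p/L.

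- Unflared leavers counted as flare-free: crude = (1 - d)p + dg, a shortfall of d(p - g).
- Unflared leavers dropped: crude = [(1 - d)p + dg] / [(1 - d) + dg].

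**Step 1: same true risk of 20% in both arms.** L = 0.2231 and g = 1 - 0.20/0.2231 = 0.1037.

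| Share lost | Counted as flare-free | Dropped |
|---|---|---|
| 10% | 0.9 × 0.20 + 0.1 × 0.1037 = 19.0% | 0.1904/0.9104 = 20.9% |
| 40% | 0.6 × 0.20 + 0.4 × 0.1037 = 16.1% | 0.1615/0.6415 = 25.2% |

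With no true difference, the first coding shows a gap of 2.9 points in favour of the arm with more exits. The second shows 4.3 points against it.

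**Step 2: a true difference.** Take risks of 15% (10% lost) and 30% (40% lost), counted as flare-free. For p = 15%, g = 0.0770 and crude = 0.135 + 0.0077 = 14.3%. For p = 30%, g = 0.1589 and crude = 0.180 + 0.0636 = 24.4%. The difference shown is about 10 points instead of 15.

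**Step 3: a risk nearer the known count.** Take p = 8/60 = 13.3%, an assumption because 8 is an interim count and 60 an estimate. Flare-free coding gives 12.7%, 12.0%, 11.4% and 10.7% for 10%, 20%, 30% and 40% lost. Dropping gives 14.0%, 14.8%, 15.8% and 17.1%. Arms losing 10% and 30% would differ falsely by 1.3 points under flare-free coding, or by 2.0 points if everyone who leaves does so at week 12.

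**Step 4: does the shortfall follow the share that leaves?** Not always. At p = 13.3%, 20% leaving at week 12 costs 2.0 points, while 30% leaving at week 42 costs 0.7. With uniform leaving, 25% risk and 15% lost costs 0.15 × (0.250 - 0.131) = 1.8 points, while 8% risk and 30% lost costs 0.30 × (0.080 - 0.041) = 1.2.

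**Step 5: Kaplan-Meier.** Under the same model, 1 minus Kaplan-Meier at week 52 targets p in each arm whatever the value of d. The planned curve does not supply this, because it pools the arms.

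**The case against.** A reader might infer that the SAP codes early leavers as flare-free, and so understates flare risk most in the arm that stops most. The documents do not support that much.

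- **The coding is not stated.** SAP 7 gives a default denominator and also provides for a missing category. The note under Table 6.3: 1 and the non-evaluable class in SAP 6.6.1 leave room for exclusion, which biases the other way. Flare-free coding is only the likelier reading.
- **The ranking of arms needs more than stopping rates.** Step 4 shows that it also depends on hazards and stopping times.
- **Stopping drug is not leaving observation.** Patients who stop because of a confirmed flare are already events. Others have an end-of-treatment visit and are invited to renal tests through week 52. The sentence that sends data to a listing stands under the CRR derivation and does not say that flares found there are ignored.
- **No exit rates are given.** The 20 on-treatment unblinded patients are not split by arm, and the placebo exemption does not say that those patients went unmeasured.
- **The numbers are small.** If 60 patients split evenly over four arms, one patient is 1/15 = 6.7 points, so a gap of 2.9 points is less than half a patient. The trial is exploratory and has no power calculation. Amendment 2 dropped the hazard ratio and its interval because flares were few.

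All of this limits the direction and size that can be claimed. It does not supply a coding rule, and it does not turn a pooled curve into a comparison by arm.

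**Conclusion.** The gap is real and worth closing. The plan compares a 52-week flare risk between arms as a crude proportion, without saying what happens to patients observed for only part of the year and without any by-arm estimate that allows for it. Counting these patients as flare-free understates the risk, and dropping them overstates it. Under both codings unequal exit can distort the comparison.

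The size is unknown. The illustrations run from about 1.3 points (13.3% risk, 10% against 30% lost) to 2.9 points (20% risk, 10% against 40% lost) under flare-free coding with uniform leaving. They rest on assumed exit rates, constant hazard, exit unrelated to flare risk and no renal data after exit. They shrink if stoppers attend the follow-up visits and those tests count. The documents do not establish that a true benefit would be reversed: with risks of 15% and 30%, the difference shrinks from 15 to about 10 points but keeps its sign.

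**What to change.** In SAP 7.5.2:

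1. Show 1 minus Kaplan-Meier at week 52 for each arm, censoring flare-free patients at their last renal assessment. Give numbers at risk and patient-years of renal follow-up, and place this beside the crude n/N.
2. State how patients whose observation ends early without a flare are coded in the crude proportion.
3. State whether flares found at post-discontinuation visits count. Reconcile this with the treatment-period limit in protocol 5.1.1 and with SAP 6.1, which assigns laboratory data up to 50 days after the last dose to the treatment period.

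The cost is SAP wording and one table from data already collected. With about 8 flares, the by-arm estimates and any intervals will be imprecise, and the Greenwood variance is zero in an arm with no flares, so the table should be read as descriptive. It also assumes non-informative censoring, which should be said beside it.

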7.7 EXTENT OF EXPOSURE

Duration of time on treatment starting with the first injection in 1293.10 to the last injection in 1293.13 will be derived for each patient & summarized by treatment group.

7.8 SAFETY ANALYSIS

All safety analyses will be performed on the treated set and performed in accordance with BI standards. Tabulations of frequencies/proportions will be used for the evaluation of categorical (qualitative) data, and tabulations of descriptive statistics will be used to analyse continuous (quantitative) data.

The format of the listings and tables will follow the BI guideline ‘Reporting of clinical trials and project summaries’ (3).

The individual values of all subjects will be listed, sorted by treatment, subject number and visit. The listings will be contained in Appendix 16.2.

7.8.1 Adverse events

AEs will be analysed using BI standards, as described in the guideline, ‘Handling and summarization of adverse event data for clinical trial reports and integrated summaries’ (4).

Unless otherwise specified, the analyses of adverse events will be descriptive in nature. All analyses of AEs will be based on the number of patients with AEs and NOT on the number of AEs.

The analysis of AEs will be based on the concept of treatment emergent AEs. This means that all AEs occurring between first drug intake and end of the residual effect period (REP) will be assigned to the randomised treatment. The residual effect period is defined as 50 days. All AEs occurring before first drug intake will be assigned to ‘Screening’ and all AEs occurring after last drug intake + 50 days will be assigned to ‘Follow-up’ (and presented in listings only). For details on the treatment definition, see [Section 6.1](#)

According to ICH E3 (5), in addition to Deaths and Serious Adverse Events, ‘other significant’ AEs need to be listed in the clinical trial report. These will be any non-serious adverse event that led to an action taken with study drug (e.g. discontinuation or dose reduced or interrupted).

Proprietary confidential information © 2021 Boehringer Ingelheim International GmbH or one or more of its affiliated companies

An overall summary of adverse events will be presented. The frequency of patients with adverse events will be summarised by treatment, primary system organ class and preferred term. Separate tables will be provided for patients with adverse events leading to treatment discontinuation, other significant adverse events according to ICH E3 (5), related adverse events and serious adverse events. AEs will also be summarised by maximum RCTC grade.

Adverse events of special interest (AESI) will be presented in tables and listings for the following:

- Injection site reactions and hypersensitivity, including anaphylaxis reaction
- Malignancies, lymphoproliferative disorders
- Severe infections and opportunistic infections
- Thromboembolism (Thrombosis and adjunct immunosuppression)
- Cytokine release syndrome
- Drug induced liver injury (DILI) (if applicable)

The system organ classes will be sorted by frequency, PTs will be sorted by frequency (within SOC).

